17. STATISTICS AND DATA ANALYSIS

17.1. Target sample size and justification

One of the key objectives of this pilot study, to inform the definitive trial, is whether patients can be successfully recruited and followed-up. We estimate that across all three sites, 24 potentially eligible ArLD patients are admitted per month. Allowing for staggered site set-up and a 7-month recruitment window, we anticipate screening ~150 patients; with a conservative recruitment rate of those screened of 60%, our recruitment target is 90 participants (~30/site).

This recruitment target will allow estimation of the overall retention rate with a 95% confidence interval (CI) of at least $\pm 11\%$. Assuming a non-differential retention rate of 75% at 6-month follow-up, indicates primary outcome data will be available from a minimum of 33 participants within each allocated group, allowing appropriate estimation of key components, such as the variability in the primary outcome, to inform the sample size calculations for the definitive trial.

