17.4. Outline of statistical analyses

Trial science outcomes, such as recruitment and retention rates, completeness of outcome measures at each follow-up, will be presented as frequencies and percentages (with confidence intervals), overall and by allocated group where relevant. The timing and frequency of missing outcome data will be summarised. Individuals lost to follow-up will be compared to those who complete the pilot study to identify any potential bias.

Descriptive statistics of the participant-reported and clinical outcomes will be produced, as appropriate for each measure for each group at all timepoints. Changes, where appropriate, between baseline and 6-months will be summarised descriptively and presented by allocated group. Interval estimates of the potential intervention effect of FIT+TAU, relative to TAU only, will be produced, with the promise of the FIT intervention (as per section 4.1, objective 2) assessed using the confidence interval for the between-group difference in change in grams of pure alcohol consumed in previous week (proposed primary outcome for definitive trial).

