3.5 SAMPLE SIZE CALCULATION

One of the key objectives of this pilot study, to inform the definitive trial, is whether patients can be successfully recruited and followed-up. We estimate that across all sites, 24 potentially eligible ArLD patients are admitted per month. Our total recruitment target is 90 participants.

This recruitment target will allow estimation of the overall retention rate with a 95% confidence interval (CI) with precision of at least $\pm 11\%$. Assuming a non-differential retention rate of 75% at the 6-month follow-up (the anticipated primary endpoint for a definitive trial), indicates primary outcome data will be available from a minimum of 33 participants within each allocated group. This will enable appropriate estimation of key components, such as the variability in the proposed primary outcome, to inform the sample size calculations for the definitive trial.

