5.3 PRELIMINARY ASSESSMENT OF FIT

As this is not a fully powered trial, it is inappropriate to perform any formal hypothesis tests comparing the allocated groups. However, to provide a preliminary assessment of whether FIT is a potentially useful treatment for patients with ArLD, we will calculate summary statistics for each of the participant-reported and clinical outcomes listed in section 0, by allocated group.

For continuous outcomes, we will produce boxplots and calculate the mean and corresponding confidence interval by allocated group for the measure at 28, 90 and 180 days and the change between baseline and 28, 90 and 180 days.

The simple, unadjusted estimated between-group difference of the change between baseline and 28, 90 and 180 days for each continuous outcome will be presented with the corresponding confidence intervals. The between-group differences, and corresponding 95% confidence intervals, adjusted for stratification variables will also be calculated using multivariable linear regression. The model will include both of the stratification variables (dichotomised baseline SADQ score and site).

For binary outcomes, we will produce calculations of the frequency and percentage (with corresponding exact 95% confidence interval) by allocated group. The unadjusted and adjusted between-group differences will be reported, derived from logistic regression models, with dichotomised baseline SADQ score and site included in the adjusted model.

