5.6 SAMPLE SIZE FOR DEFINITIVE TRIAL

One of the key purposes of a pilot study is to obtain data to inform the sample size calculation for a definitive trial. To assist with future sample size calculations, we will calculate, overall and by allocated group:

- the standard deviation for the proposed primary outcome of alcohol consumption (grams consumed of pure alcohol in the previous week)
- the correlation coefficient between baseline and (i) 180 day assessment and (ii) change between baseline and 180 day assessment for the proposed primary outcome of grams consumed of pure alcohol in the previous week

Point estimates will be presented alongside two-sided 80% and 90% confidence intervals.

Indicative sample sizes for a definitive trial with alcohol use at 180 days as the primary outcome will then be produced, conservatively using the upper bounds from the confidence intervals for the estimated standard deviation. Additional sample size scenarios will consider adjustment for baseline alcohol use (i.e. using an analysis of covariance approach) and will use the lower bound from the confidence intervals for the correlation coefficient.

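### The interval used to judge the promise of FIT leaves out baseline alcohol use, and is generally wider than a baseline-adjusted interval from the same data would be

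*SAP*

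**What the plan says.** Protocol 17.4 ties the promise of FIT (primary objective 2) to the confidence interval for the "between-group difference in change in grams of pure alcohol consumed in previous week".

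SAP 5.3 gives two estimates of it. The first is "The simple, unadjusted estimated between-group difference of the change between baseline and 28, 90 and 180 days for each continuous outcome". The second is a multivariable linear regression, of which the SAP says: "The model will include both of the stratification variables (dichotomised baseline SADQ score and site".

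The table shells in SAP Appendix A match. Tables 16 and 17 hold differences in change from baseline, unadjusted and adjusted for those two factors. Tables 14 and 15 hold differences in the follow-up values, again unadjusted and adjusted for the same two factors. All four show 75%, 85% and 95% intervals.

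SAP 3.4.3 (Table 1) collects alcohol use, SADQ, WEMWBS and SWEMWBS at baseline and at days 28, 90 and 180. No effect model uses the continuous baseline value. Analysis of covariance appears only in SAP 5.6, for sizing the later trial: "Additional sample size scenarios will consider adjustment for baseline alcohol use (i.e. using an analysis of covariance approach".

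**The concern.** Subtracting baseline from follow-up fixes the slope on baseline at 1. If the true slope is well below 1, the subtraction adds baseline noise to the outcome. A low slope is plausible here. Baseline is the week before hospital admission in patients selected for high consumption, while some participants may be abstinent at follow-up (SAP Table 11b counts them). The documents give no correlation, so this remains a supposition.

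What is at stake is precision. With about 33 evaluable participants per arm, the width of the interval largely determines how much the preliminary assessment of FIT can say. A covariate that is already collected could narrow it.

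**Working it through.** **The plan's own figures.** Protocol 17.1 expects about 150 screened: "with a conservative recruitment rate of those screened of 60%, our recruitment target is 90 participants", and 150 × 0.60 = 90. SAP 3.5 continues: "Assuming a non-differential retention rate of 75% at the 6-month follow-up", giving 90 × 0.75 / 2 = 33.75, in line with "primary outcome data will be available from a minimum of 33 participants within each allocated group". The stated retention precision of ±11% is also met: 1.96 × √(0.5 × 0.5 / 90) = 10.3 points, or 10.7 by the exact method at 45/90. The documents state no width for the FIT-effect interval.

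**Inputs not in the documents (assumed).** The correlation r between baseline and day-180 alcohol use, from 0 to 0.95. The ratio k = SD at day 180 / SD at baseline, from 0.5 to 2. SAP 5.6 plans to estimate both SDs and the correlation.

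**Formulas.** With the baseline SD set to 1, the standard error of the group difference is √(2/33) times:

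- change score: √(1 + k² − 2rk)
- follow-up value only: k
- baseline-adjusted (ANCOVA): k√(1 − r²)

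The change-score variance minus the ANCOVA variance is (1 + k² − 2rk) − k²(1 − r²) = (1 − rk)². This is never negative, and is zero only when the slope rk equals 1. With k = 1 the variance ratio is 2(1 − r)/(1 − r²) = 2/(1 + r). At r = 0.3 that is 1.54, so the standard error is 24% larger, and 66 change scores carry the information of 66/1.54 ≈ 43 baseline-adjusted observations.

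**Small-sample cost.** Intercept, arm, three sites (Protocol 7) and SADQ band use 5 parameters, leaving 66 − 5 = 61 degrees of freedom. Adding baseline leaves 60. ANCOVA also takes a factor √(1 + 1/59) for estimating the slope. SAP Table 3 has four site rows; a fourth site would take one more degree of freedom from each model and barely move the ratios.

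**95% half-widths, k = 1, 33 per arm, in SD units**

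| r | Change score | Follow-up only | ANCOVA | Change vs ANCOVA | Follow-up vs ANCOVA |
|---|---|---|---|---|---|
| 0 | 0.696 | 0.492 | 0.497 | 40% wider | 1% narrower |
| 0.2 | 0.623 | 0.492 | 0.487 | 28% wider | 1% wider |
| 0.3 | 0.582 | 0.492 | 0.474 | 23% wider | 4% wider |
| 0.5 | 0.492 | 0.492 | 0.430 | 14% wider | 14% wider |
| 0.7 | 0.381 | 0.492 | 0.355 | 7% wider | 39% wider |
| 0.9 | 0.220 | 0.492 | 0.216 | 2% wider | 128% wider |

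The 85% and 75% intervals scale almost identically. Without the small-sample cost, follow-up only against ANCOVA is 1/√(1 − r²): about 5% wider at r = 0.3 and 25% at r = 0.6.

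**Unequal SDs (ANCOVA width / change-score width, cost included).** At k = 0.75 the ratio lies between 0.60 and 0.76 for r from 0 to 0.95. At k = 1.25 it is 0.89 at r = 0.3, 0.95 at 0.5, 1.00 at 0.7 and 1.01 at 0.8, where the slope is exactly 1.

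**Single trials.** In 1,500 simulated trials per scenario with normal outcomes, ANCOVA gave the narrower interval than the change score in 99.9% at r = 0.3, 99.3% at 0.5, 94.7% at 0.7 and 63% at 0.9 (k = 1). At k = 1.25 it did so in only 41% at r = 0.7 and 19% at r = 0.8.

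**The case against.** The strongest counter-argument is that change scores are not the only planned estimates. Tables 14 and 15 compare follow-up values, and the weaker the correlation, the closer they come to ANCOVA. This stands, and it rules out the reading that every planned interval is too wide. It does not remove the point: Protocol 17.4 names the change interval as the evidence of promise, and the follow-up-only intervals lose ground as the correlation rises.

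Three other inferences are tempting, and the documents do not support them:

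- *That regression to the mean biases the planned estimate.* Under randomisation it acts equally on both arms in expectation. Only chance baseline imbalance in the realised sample remains, and adjustment deals with that.
- *That the pilot estimates a different effect from the one the definitive trial would use.* Change score, follow-up difference and linear ANCOVA all target the same mean difference. The proposed primary outcome is itself a change, and SAP 5.6 offers ANCOVA only as an additional sizing scenario.
- *That a go/no-go decision turns on this.* No criterion in SAP Table 2 uses the interval, no hypothesis test is planned (SAP 4.3), and Protocol 17.4 sets no threshold for promise.

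Timing also matters. The SAP revision table records changes made after database lock and data export, by statisticians who were not blinded. Making a new model the headline now would displace the interval that Protocol 17.4 specified. That objection stands, and it limits the fix to an added estimate.

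**Conclusion.** The point holds as a matter of precision, not of bias or validity. The interval chosen to judge promise is in expectation generally wider than a baseline-adjusted one. With equal SDs and 33 per arm the excess runs from about 28% at r = 0.2 to 2% at r = 0.9, and it vanishes near a slope of 1. The excess is larger if baseline is the more variable measure. Neither planned estimator is efficient over the whole range: the change score does badly at low correlation and the follow-up value at high correlation. ANCOVA is never more than about 1% wider than the better of the two in the scenarios examined.

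The size rests on an assumed correlation and SD ratio, on 33 per arm, and on a linear, roughly normal outcome. Many zero values at follow-up would alter the figures. It is a worthwhile, low-cost addition, and no formal decision rule in the plan depends on it.

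**What to change.** In SAP 5.3 and Tables 15 and 17, add one model for each continuous outcome that has a baseline (alcohol use, SADQ, WEMWBS, SWEMWBS):

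follow-up value = arm + continuous baseline value of that outcome + site + SADQ band

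Report it with 75%, 85% and 95% intervals at days 28, 90 and 180. Once baseline is in the model, analysing change or follow-up value gives the same arm estimate and interval, so one added row serves both tables. The urinary metabolites are measured only at day 180 and stay as planned.

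Label the model as added after database lock. Show it beside the change-score interval of Protocol 17.4, and keep all the planned estimates. SAP 5.6 needs no change, since it already covers the SDs, the correlation and ANCOVA sizing scenarios.

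The cost is some SAP wording, one degree of freedom, and one further post hoc estimate for readers to weigh. No new data are needed and no Table 2 criterion changes.

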5.4 SAFETY DATA

The likelihood of participants being harmed by either the FIT intervention or any of the trial procedures is very low. As such, the reporting of adverse events in the MIRAGE trial is restricted to only those events that are serious, which

- results in death
- Is life-threatening
- Requires inpatient hospitalisation or prolongation of existing hospitalisation
- Results in a persistent or significant disability/incapacity
- Is a significant or important medical event

All serious adverse events reported after the participant has consented to take part in the trial will be reported by treatment group, whereby any participant who has received at least one FIT session will be included in the TAU + FIT treatment group.

5.5 PROGRESSION TO DEFINITIVE TRIAL

The progression criteria in Table 2 are proposed for consideration as part of the decision on whether or not to progress to planning a definitive trial. If the study delivers results on all of the progression criteria in the green column, it is intended that this will result in the planning of a definitive trial. If some criteria are in the amber column, modification of the trial design will be required before considering progression. If some criteria fall in the red column, the trial team will consider all options, including not progressing to a definitive trial.

Criteria	Red	Amber	Green
Percentage recruited from patients approached by research team (for discussion of informed consent)	<40	40 – 60	>60
Percentage of intervention participants completing FIT session 1 and at least one of FIT session 2 or FIT session 3	<50	50 – 70	>70
Percentage of all participants followed-up at proposed primary endpoint of 180 days	<60	60 – 80	>80
Percentage of all participants providing valid data for the proposed primary outcome of alcohol use at proposed primary endpoint of 180 days	<55	55 – 75	>75

Table 2: Proposed progression criteria for planning a definitive trial

5.6 SAMPLE SIZE FOR DEFINITIVE TRIAL

One of the key purposes of a pilot study is to obtain data to inform the sample size calculation for a definitive trial. To assist with future sample size calculations, we will calculate, overall and by allocated group:

- the standard deviation for the proposed primary outcome of alcohol consumption (grams consumed of pure alcohol in the previous week)
- the correlation coefficient between baseline and (i) 180 day assessment and (ii) change between baseline and 180 day assessment for the proposed primary outcome of grams consumed of pure alcohol in the previous week

Point estimates will be presented alongside two-sided 80% and 90% confidence intervals.

Indicative sample sizes for a definitive trial with alcohol use at 180 days as the primary outcome will then be produced, conservatively using the upper bounds from the confidence intervals for the estimated standard deviation. Additional sample size scenarios will consider adjustment for baseline alcohol use (i.e. using an analysis of covariance approach) and will use the lower bound from the confidence intervals for the correlation coefficient.

5.7 STATISTICAL SOFTWARE

The statistical analyses will be undertaken using StataSE version 16 or later, supplemented where required by R.

[figure not shown]

APPENDIX A: PLOTS AND TABLES

Examples of potential tables and plots to be used in the statistical analysis report.

*TAU may be completed before recruitment, post recruitment or after baseline assessment.

Figure 2: CONSORT diagram of participant flow through the MIRAGE Pilot Trial

Table 3: Number of participants who completed TAU before recruitment, post recruitment or after baseline assessment

Site	Before recruitment N (%)	Post recruitment but before baseline assessment N (%)	Post baseline assessment N (%)
1			
2			
3			
4			
Total			

Table 4: Number of assessments completed within the scheduled 28, 90, and 180-day assessment windows

Assessments Completed	TAU N (%)	FIT + TAU N (%)	ALL N (%)
28-day window (± 7 days)			
90-day window (± 7 days)			
180-day window (± 14 days)			

Table 5: Time differences between key events

Time Elapsed (days) Between	TAU Mean (SD) [range]	FIT + TAU Mean (SD) [range]	ALL MEAN (SD) [range]
Baseline and randomisation			
Randomisation and start of the FIT sessions*	N/A		
Randomisation and 28 (± 7) days post baseline assessment			
Randomisation and 90 (± 7) days post baseline assessment			
Randomisation and 180 (± 14) days post baseline assessment			
Last FIT session attended and 180 (± 14) days post baseline assessment*	N/A		

* FIT participants only

Table 6: Number of participants attending the recommended number of FIT sessions before the assessments

Number of Participants	FIT + TAU N (%)
Attended ≥ 4 FIT sessions before 28 (± 7) day assessment	
Attended ≥ 7 FIT sessions before 90 (± 7) day assessment	
Attended ≥ 9 FIT sessions before 180 (± 14) day assessment	
Attended final FIT session after 180 (± 14) day assessment	

Table 7: Acceptability and adherence to the FIT intervention

Fit Session	Completed total N (%)	Completed within specified timeframe N (%)	Cumulative total of completion N (%)	Cumulative total of completion within specified timeframe N (%)
1 (in-patient)				
2 (face-to-face or telephone)				
3 (telephone)				
4 (telephone)				
5 (telephone)				
6 (telephone)				
7 (telephone)				
8 (telephone)				
9 (telephone)				
Total				

Table 8a: Completeness of proposed primary and secondary outcomes

Outcome	Time Point	TAU			FIT + TAU			All		
		Number (%) of Participants			Number (%) of Participants			Number (%) of Participants		
		Attended Visit	Completed All Items	With Valid Score	Attended Visit	Completed All Items	With Valid Score	Attended Visit	Completed All Items	With Valid Score
Alcohol Use (grams of pure alcohol/ week)*	Baseline									
	28 (±7) days									
	90 (±7) days									
	180 (±14) days									
SADQ Score	Baseline									
	28 (±7) days									
	90 (±7) days									
	180 (±14) days									
WEMWBS	Baseline									
	28 (±7) days									
	90 (±7) days									
	180 (±14) days									
SWEMWBS	Baseline									
	28 (±7) days									
	90 (±7) days									
	180 (±14) days									
Re-hospitalisation	180 (±14) days		N/A			N/A			N/A	

* completeness of Timeline Follow-Back data, used by the Research Nurses to calculate Alcohol Use, is summarised below in Table 8b.

Table 9b: Completeness of timeline follow-back data (used to calculate proposed primary outcome of alcohol use)

Timeline Follow-Back data collection	Days before visit	TAU Number (%) of Participants				FIT + TAU Number (%) of Participants				All Number (%) of Participants			
		With Completed Units of Alcohol Data	Reason not collected			With Completed Units of Alcohol Data	Reason not collected			With Completed Units of Alcohol Data	Reason not collected		
			Could not remember	Not asked about alcohol	Other		Could not remember	Not asked about alcohol	Other		Could not remember	Not asked about alcohol	Other
Baseline	1												
	2												
	3												
	4												
	5												
	6												
	7												
28 (±7) days	1												
	2												
	3												
	4												
	5												
	6												
	7												
90 (±7) days	1												
	2												
	3												
	4												
	5												
	6												
	7												
180 (±14) days	1												
	2												
	3												
	4												
	5												
	6												
	7												

Table 10: Summary statistics of baseline and demographic participant characteristics

	TAU (n=)	FIT + TAU (n=)	All (n=)
Age			
Mean (SD) [range]			
Median (IQR)			
AUDIT Score			
Mean (SD) [range]			
Median (IQR)			
Gender n (%)			
Male			
Female			
Living Arrangements n (%) *			
Alone			
Spouse/Partner			
Parent/s			
Sibling/s			
Child/ren			
Rather not say			
Other			
Ethnicity n (%)			
White			
Asian			
Black			
Mixed/Multiple			
Other			
Place of Residence n (%) *			
Flat/Apartment			
House/Bungalow			
Residential/Care Home			
Other			

Occupation Status n (%) *			
Unemployed			
Student			
Part time work			
Full time work			
Age retired			
Medically Retired			
Other			
Year of diagnosis			
Mean (SD) [range]			
Median (IQR)			
Stage of Liver Disease n (%)			
Fatty			
Fibrosis			
Cirrhosis			
Child-Pugh Score			
Mean (SD) [range]			
Median (IQR)			
MELD Score			
Mean (SD) [range]			
Median (IQR)			

*Participants can provide data in more than one category – percentages will not necessarily add to 100%

Table 10: Summary statistics for the proposed primary and secondary outcome measures by allocated group

Variable	Time point	TAU			FIT + TAU		
		N	Mean (SD) (95% CI)/Median [IQR]	Range	N	Mean (SD) (95% CI) /Median [IQR]	Range
Alcohol Use (grams of pure alcohol/ week)	baseline						
	28 (±7) days						
	90 (±7) days						
	180 (±14) days						
SADQ Score	baseline						
	28 (±7) days						
	90 (±7) days						
	180 (±14) days						
WEMWBS	baseline						
	28 (±7) days						
	90 (±7) days						
	180 (±14) days						
SWEMWBS	baseline						
	28 (±7) days						
	90 (±7) days						
	180 (±14) days						
Ethyl Glucuronide (µg/L)	180 (±14) days						
Ethyl Sulphate (µg/L)	180 (±14) days						
Re- hospitalisation*	180 (±14) days						

* Rates and corresponding confidence intervals given for re-hospitalisation

Table 11: Summary statistics for the changes between baseline and 28, 90, and 180 day assessments for proposed primary and secondary outcomes including only those participants who complete all follow-up visits

Variable	Time point	TAU			FIT + TAU		
		N	Mean (SD) Change From Baseline (95% CI)/Median [IQR]	Range	N	Mean (SD) Change From Baseline (95% CI) /Median [IQR]	Range
Alcohol Use (grams of pure alcohol/ week)	28 (±7) days						
	90 (±7) days						
	180 (±14) days						
SADQ Score	28 (±7) days						
	90 (±7) days						
	180 (±14) days						
WEMWBS	28 (±7) days						
	90 (±7) days						
	180 (±14) days						
SWEMWBS	28 (±7) days						
	90 (±7) days						
	180 (±14) days						

Table 11b: Proportion of participants who completed TLFB assessment and with no alcohol consumption as calculated from TLFB

Variable	Time point	TAU	FIT + TAU
		N (% of participants with complete TLFB)	N (% of participants with complete TLFB)
Participants with zero alcohol consumption	Baseline		
	28 (±7) days		
	90 (±7) days		
	180 (±14) days		

Table 12: Re-hospitalisations by allocated group

Re-hospitalisation	TAU N (%)				FIT + TAU N (%)			
	0	1	2	>2	0	1	2	>2
No. of re-admissions								
By 28 (± 7) days								
By 90 (± 7) days								
By 180 (± 14) days								

Table 13: Proportion of participants who relapse and time to relapse to alcohol use by allocated group

	TAU	FIT + TAU
N (%) who relapsed by:		
28 (± 7) days		
90 (± 7) days		
180 (± 14) days		
Time to relapse (days)	Median (Inter-quartile Range) [Range]	Median (Inter-quartile Range) [Range]

Table 14: Unadjusted between-group differences and confidence intervals for proposed primary and secondary outcome measures, with unadjusted confidence intervals

Variable	Time Point	Mean Between-group Difference	Unadjusted 95% CI	Unadjusted 85% CI	Unadjusted 75% CI
Alcohol Use (grams of pure alcohol/ week)	28 (± 7) days				
	90 (± 7) days				
	180 (± 14) days				
SADQ Score	28 (± 7) days				
	90 (± 7) days				
	180 (± 14) days				
WEMWBS	28 (± 7) days				
	90 (± 7) days				
	180 (± 14) days				
SWEMWBS	28 (± 7) days				
	90 (± 7) days				
	180 (± 14) days				
Ethyl Glucuronide ($\mu\text{g/L}$)	180 (± 14) days				
Ethyl Sulphate ($\mu\text{g/L}$)	180 (± 14) days				
Re-hospitalisation*	180 (± 14) days				

* Rates and corresponding confidence intervals given for re-hospitalisation

Table 15: Between-group differences and confidence intervals for proposed primary and secondary outcome measures, adjusted for stratification variables (dichotomised baseline SADQ score and site)

Variable	Time Point	Adjusted Mean Between-group Difference	Adjusted 95% CI	Adjusted 85% CI	Adjusted 75% CI
Alcohol Use (grams of pure alcohol/ week)	28 (± 7) days				
	90 (± 7) days				
	180 (± 14) days				
SADQ Score	28 (± 7) days				
	90 (± 7) days				
	180 (± 14) days				
WEMWBS	28 (± 7) days				
	90 (± 7) days				
	180 (± 14) days				
SWEMWBS	28 (± 7) days				
	90 (± 7) days				
	180 (± 14) days				
Ethyl Glucuronide ($\mu\text{g/L}$)	180 (± 14) days				
Ethyl Sulphate ($\mu\text{g/L}$)	180 (± 14) days				
Re-hospitalisation*	180 (± 14) days				

* Rates and corresponding confidence intervals given for re-hospitalisation

Table 16: Unadjusted between-group differences and confidence intervals of change from baseline for proposed primary and secondary outcomes

Variable	Time Point	Mean Between-group Difference of Change From Baseline	Unadjusted 95% CI	Unadjusted 85% CI	Unadjusted 75% CI
Alcohol Use(grams of pure alcohol/ week)	28 (± 7) days				
	90 (± 7) days				
	180 (± 14) days				
SADQ Score	28 (± 7) days				
	90 (± 7) days				
	180 (± 14) days				
WEMWBS	28 (± 7) days				
	90 (± 7) days				
	180 (± 14) days				
SWEMWBS	28 (± 7) days				
	90 (± 7) days				
	180 (± 14) days				
Ethyl Glucuronide ($\mu\text{g/L}$)	180 (± 14) days				
Ethyl Sulphate ($\mu\text{g/L}$)	180 (± 14) days				

Table 17: Between-group differences and confidence intervals for of change from baseline for proposed primary and secondary outcome measures, adjusted for stratification variables (dichotomised baseline SADQ score and site)

Variable	Time Point	Adjusted Mean Between-group Difference of Change From Baseline	Adjusted 95% CI	Adjusted 85% CI	Adjusted 75% CI
Alcohol Use (grams of pure alcohol/ week)	28 (± 7) days				
	90 (± 7) days				
	180 (± 14) days				
SADQ Score	28 (± 7) days				
	90 (± 7) days				
	180 (± 14) days				
WEMWBS	28 (± 7) days				
	90 (± 7) days				
	180 (± 14) days				
SWEMWBS	28 (± 7) days				
	90 (± 7) days				
	180 (± 14) days				
Ethyl Glucuronide ($\mu\text{g/L}$)	180 (± 14) days				
Ethyl Sulphate ($\mu\text{g/L}$)	180 (± 14) days				

Table 18: Estimates of standard deviations of proposed primary outcome (alcohol use) for informing sample size calculations for a definitive trial

Parameter	Point Estimate	80% CI*	90% CI*
Standard deviation of alcohol use at baseline			
Standard deviation of alcohol use at 180 (± 14) days assessment			
Standard deviation of change in alcohol use between baseline and 180 (± 14) days assessment			

* upper bound of two-sided confidence interval relevant as conservative estimate for sample size calculations

Table 19: Estimates of correlation coefficients for proposed primary outcome (alcohol use) for informing sample size calculations for a definitive trial

Parameter	Point Estimate	80% CI*	90% CI*
Correlation coefficient between baseline and 180 (± 14) days assessment of alcohol use			
Correlation coefficient between baseline and change between baseline and 180 (± 14) days assessment of alcohol use			

* lower bound of two-sided confidence interval relevant as conservative estimate for sample size calculations

